| Diagnosis and Main Inclusion Criteria | 
Inclusion Criteria:
 
 • Age over 18 years • Patients diagnosed with clinically localized prostate cancer • Low or Low-intermediate Risk Prostate cancer¹ defined as: 
 ◦ Pre-operative PSA \leq 20.0 ng/ml ◦ Clinical stage cT1 or cT2 ◦ Gleason score 3+3 or 3+4 • Patients choosing AS or already on AS as primary management strategy • No previous treatment for prostate cancer with radiotherapy, chemotherapy, or hormonal therapy • No contraindications for gadolinium enhanced MRI |
| Study Imaging | Standard multiparametric prostate MRI with high resolution diffusion weighted imaging |
| Control Imaging | Standard multiparametric prostate MRI |
| Reference standard | Evidence of disease progression on standard 12-core ultrasound-guided prostate biopsy. |
| Statistical analysis | 
Our hypothesis is that changes in tumor size or apparent diffusion coefficient (ADC) on high resolution MRI will predict presence of biopsy criteria for disease progression.
 
59 patients achieve 91% power to detect a 0.285 cm^3 difference (between patients progressing and patients not progressing) in the mean change in tumor volume at the two-sided two-sample t-test with a 0.05 level of significance. With respect to change in ADC, 59 patients achieve 80% power to detect a difference in the mean change ADC around 0.07 at the two-sided two-sample t-test with a 0.05 level of significance. This corresponds to about a 50% increase in ADC between the two groups of patients.
 |

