- Improved imaging resolution will allow for **more accurate measurement of tumor size and ADC, and detection of small changes in size or grade over time.** Standard prostate DWI has poor resolution; therefore, tumor growth kinetics have never been accepted as clinical criteria for cancer progression while on AS. If tumor growth kinetics or changes in grade determined by ADC prove prognostic, AS can rely less on serial transrectal biopsies, which can lead to serious complications.

Prostate Cancer

Prostate cancer is the most commonly diagnosed cancer among men and the second leading cause of cancer death in US men.¹² In the US, there are more than 200,000 newly diagnosed cases and nearly 40,000 deaths from prostate cancer annually. The lifetime risk of developing prostate cancer is one in seven men.¹³ The vast majority of men diagnosed with prostate cancer do not die of their disease even when curative therapy is not administered.^{14, 15} However, historically approximately 90% of men diagnosed with localized prostate cancer elect therapies such as radical prostatectomy or radiotherapy.¹⁶ The problem is that definitive therapies for prostate cancer can negatively impact quality-of-life by producing side-effects such as permanent urinary incontinence (7-14% post-treatment) and erectile dysfunction (44-51% post-treatment).¹⁷ Therefore overtreatment of prostate cancer has broad impact on quality of life and health care costs. The U.S. Preventive Services Task Force (USPSTF) recommends against PSA-based screening for all U.S. men; they argue that screening provides little to no benefit for most men while harming many men.¹⁸ On the other hand, the American Urologic Association (AUA) maintains that prostate cancer screening and risk assessment should be offered to asymptomatic men 55-69 years of age.¹⁹

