Both opponents and advocates of PSA-based screening acknowledge that screening increases the detection of prostate cancer. An important assumption underlying the USPSTF recommendation against screening is that men with indolent cancer will continue to receive unnecessary treatment. An important assumption underlying the AUA recommendation for screening is that patients and physicians will be able to uncouple the diagnosis of prostate cancer from treatment. For example, men at highest risk for death from prostate cancer will receive treatment. All other men will undergo a period of active surveillance (AS). During followup on AS, men with evidence of high risk disease or cancer progression are offered definitive local therapy; however, men who continue to have low risk cancer can delay or completely avoid treatment. A barrier to AS is that clinical tools for risk-stratifying and monitoring men with newly diagnosed prostate cancer have limited accuracy. Prostate cancers are multifocal and biopsies are vulnerable to sampling error. Transrectal ultrasound-guided (TRUS) biopsy remains the gold standard for diagnosing prostate cancer and monitoring patients on AS. However, the standard prostate biopsy may miss clinically significant disease. TRUS biopsy understages the cancer in approximately a third of patients.^{20, 21} Furthermore, TRUS biopsy is accompanied by complications such as systemic infection, bleeding, and transient erectile dysfunction.²² **There is a clear need for innovations to reduce the clinical burden of diagnosing and monitoring prostate cancer.**

3.0 STUDY DESIGN:

A. Overview

Prostate cancer is the rare malignancy where there is no imaging strategy to serially monitor the tumor. MRI, which is the best tool we have for imaging the prostate, cannot detect most tumors and does not have the resolution to detect subtle changes in tumor size or tumor characteristic. Therefore, followup during AS relies on serial transrectal biopsies. An effective imaging strategy will decrease the clinical burden of AS. This prospective trial will compare the effectiveness of high resolution MRI (hrMRI) and standard MRI (sMRI) for serially monitoring prostate tumors for clinical progression, which is an indication for definitive local therapies such as radical prostatectomy and external beam radiotherapy. **We test the hypothesis that hrMRI may detect changes in tumor size or ADC value, which will predict clinical progression as defined by biopsy criteria.**

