Preliminary data from 13 patients with a total of 14 Gleason score 6 lesions show a mean of 0.19 cm³ and standard deviation of 0.19 cm³. We expect to detect at least a 50% increase in tumor volume in the group who progress compared to the group of patients that do not progress relative to baseline. Assuming that the standard deviation at the biopsy/MRI is similar to the baseline biopsy/MRI, group sample sizes of 12 patients who progressed and 47 patients that do not progress achieve 91% power to detect a difference in the mean change tumor volume around 0.285 cm³ at the two-sided two-sample t-test with a 0.05 level of significance. The estimate standard deviation of the difference in tumor size in each group (SDdiff) was estimated assuming the correlation coefficient measurements is 0. Since this correlation coefficient is likely to be positive, this power calculation is very conservative and much smaller mean change tumor volume can be detected. In fact, if this correlation coefficient equals to 0.6, then we can achieve 90% power to detect a mean change tumor volume around 0.18 cm³. With respect to change in ADC, preliminary data show that the mean and SD of ADC are 0.2 and 0.05, respectively. Under similar assumptions for the correlation coefficient between the first and second measurements (corr = 0), group sample sizes of 12 patients who progressed and 47 patients that do not progress achieve 80% power to detect a difference in the mean change ADC around 0.07 at the two-sided two-sample t-test with a 0.05 level of significance. This corresponds to about a 50% increase in ADC between the two groups of patients.

Multivariable logistic regression model will be used to study the association between change in tumor size and ADC from the first and the second biopsy as assessed by imaging and disease progression adjusting for potential baseline characteristics such as PSA level, clinical stage, NCCN risk category, and size of prostate nodule. Tumor size

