and ADC is measured by averaging the volumes or ADCs of all detectable lesions (PI-RADS 3 - 5). Secondary analyses include studying this association by considering changes of single lesions. Automatic variable selection methods such as backward and stepwise selection will be used as a guideline to identify sets of important predictors of progression. More rigorous approach based on a 4-step procedure outlined in Collett²⁴ will be employed. Several model checking diagnostics will be employed to ensure that the logistic model is appropriate.²⁵

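### The size-or-ADC hypothesis rests on an incompletely specified, unpenalised logistic model with 12 planned progressors and no rule for two markers: about a 9–10% chance of a false claim (11–14% with likelihood-ratio tests), and log odds ratios that tend to run high

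*Combined protocol and SAP*

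**What the plan says.** The Study Summary states the hypothesis that "changes in tumor size or apparent diffusion coefficient (ADC) on high resolution MRI will predict presence of biopsy criteria for disease progression". Section 3.0 A repeats it as something to be tested: "We test the hypothesis that hrMRI may detect changes in tumor size or ADC value". Either marker is enough to meet it.

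The power text in section 3.0 G rests on "group sample sizes of 12 patients who progressed and 47 patients that do not progress". It gives each marker its own two-sided t-test at 0.05, with 91% power for volume and 80% for ADC. The Study Summary lists 80 subjects. Section 3.0 G takes a 20% progression rate and calls it conservative.

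The only analysis then described is the logistic model: "Multivariable logistic regression model will be used to study the association between change in tumor size and ADC" and progression, "adjusting for potential baseline characteristics such as PSA level, clinical stage, NCCN risk category, and size of prostate nodule". On model building the plan adds: "Automatic variable selection methods such as backward and stepwise selection will be used as a guideline to identify sets of important predictors of progression". It continues: "More rigorous approach based on a 4-step procedure outlined in" a cited textbook, whose steps are not set out, and it promises model diagnostics. Single-lesion analyses are labelled secondary.

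The section does not state:
- which test judges each marker;
- an entry or removal level for selection;
- whether both imaging terms stay in the model;
- any shrinkage;
- how the 0.05 level is shared between the markers.

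**The concern.** The trial is sized with two unadjusted t-tests but analysed with a model of at least six candidate terms and 12 expected events. A hypothesis that either of two markers can satisfy, each at 0.05, has a familywise error above 5%. Separately, maximum likelihood with about two events per candidate tends to push log odds ratios away from zero. A marker reported only because selection kept it carries further inflation.

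The Background shows what is at stake: "If tumor growth kinetics or changes in grade determined by ADC prove prognostic, AS can rely less on serial transrectal biopsies". An overstated odds ratio, or about twice the nominal chance of a false positive, bears directly on that inference.

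**Working it through.** **Inputs from the documents.** 12 progressors and 47 non-progressors; 80 enrolled; 20% progression; volume SD 0.19 cm³ and difference 0.285 cm³; ADC SD 0.05 and difference 0.07; correlation 0 between the two measurements; two-sided 0.05 for each marker.

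**The plan's own power.** SD of change = 0.19 × √2 = 0.2687 cm³, so the volume effect is 0.285 / 0.2687 = 1.06 SD. A two-sample t-test at 12 vs 47 has power 90.6% (normal approximation) or 89.7% (exact t), against the stated 91%. For ADC, 0.07 / (0.05 × √2) = 0.99 SD gives 85%. The stated 80% corresponds to 0.065, which rounds to the plan's figure of around 0.07.

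**Events per candidate.** Two imaging terms plus four named baseline terms make six. 12 / 6 = 2.0. If all 80 are evaluable, 0.20 × 80 = 16 events and 16 / 6 = 2.7. The list of adjusters is open-ended, so six is a minimum.

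**Assumptions for the simulations (not in the documents).** Baseline covariates are independent; size, ADC, PSA and nodule size are normal; stage and risk category are binary (0.3 and 0.4). Effects are mean shifts in SD units, so the true log odds ratio per SD equals the shift. There were 6,000–8,000 data sets per scenario, with further independent runs; ranges cover all of them.

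**(a) Chance of a false either-marker claim, neither marker related to progression.**
- Two independent 5% tests: 1 − 0.95² = 9.75%.
- Six-term maximum likelihood, Wald tests: about 9–10%.
- Six-term maximum likelihood, likelihood-ratio tests: about 11–14%.
- Backward selection at p<0.05 (12/47 and 16/64): 8.7–9.3% Wald and 11.4–11.8% likelihood ratio, no higher than without selection.
- Six-term maximum likelihood with Holm, 12/47: 4.2% Wald, 7.1% likelihood ratio.

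**(b) Overstatement in the six-term maximum-likelihood fit, true log odds ratio 1.06.**
- 12/47: median overstated by about 17–21% (for example 1.26 / 1.06 = 1.19).
- 16/64: about 13–15% (for example 1.20 / 1.06 = 1.13).
- Fewer terms at 12/47: about 15% with four, 7% with two.
- Firth-penalised fits: medians 0.99–1.05.

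**(c) Reporting only what selection keeps.** Section 3.0 G expects at least a 50% increase in volume. Half of 0.19 is 0.095 cm³, and 0.095 / 0.2687 = 0.35 SD. With a true log odds ratio of 0.35, size is kept at p<0.05 in 17–20% of data sets at 12/47. When it is kept, its estimate averages about 0.9–1.0. A Firth estimate looked at only when p<0.05 also averages about 0.9. Reported in every data set, Firth averages 0.35.

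**(d) Proposed analysis: Firth, two markers and two adjusters, penalised likelihood-ratio test, Holm.** Null either-marker error is 4.4% at 12/47 and 4.7% at 16/64. Without Holm, six-term Firth gives 8.6%, so penalisation alone does not settle (a).

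**The case against.** The strongest case against runs as follows. Stepwise selection is only a guideline, and a procedure described as more rigorous will be used with diagnostics. The logistic model is said to study an association, and the only tests named at 0.05 are the t-tests in the power text. Formal multiplicity control in a single-arm, single-centre imaging study is partly a matter of judgement. Enrolment is 80, and 20% progression is called conservative, so more than 12 events may accrue.

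Some of this stands. That the logistic model is the confirmatory test is an inference, although no other analysis is described and section 3.0 A says that a hypothesis is tested. More events shrink the bias: with an assumed 30% progression (24/56) the median overstatement is about 12%. The cited steps cannot be seen, so they can be neither faulted nor credited with error control.

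Three stronger readings are tempting, and the documents do not support them:
- *Sparse events and stepwise selection cause the raised false-claim rate.* Most of it is plain two-marker testing. Selection adds nothing, and only likelihood-ratio testing with few events adds a few points. The plan does not name that test.
- *Every reported odds ratio will be about 20% too high on the log scale.* That describes one case, an unselected six-term fit at 12 events, and the plan may report a smaller model.
- *Firth penalisation cures selection inflation.* It does not. Conditioning on significance inflates any estimator.

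**Conclusion.** The point holds as two separate problems.

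The either-marker error is about 9–10%, and about 11–14% if likelihood-ratio tests are used in the six-term model. The 9.75% benchmark needs only the two 0.05 levels and independence of the tests.

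The estimation bias is conditional. It assumes ordinary maximum likelihood with all six terms, independent covariates and a true log odds ratio of 1.06 per SD. It is then about 17–21% at 12/47 and 13–15% at 16/64, and less with fewer terms. Independence is a simplification, because eligibility defines the risk group partly from PSA and stage. The larger inflation of small effects comes from reporting only what is significant, and is avoided by always reporting both terms.

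This should be corrected before analysis. It does not invalidate the design.

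**What to change.** For the test of the stated hypothesis, the SAP should:
- pre-specify one logistic model without automatic selection;
- keep and report both imaging terms whatever their p-values;
- name a short adjuster set in advance (for example NCCN risk category and nodule size);
- fit by Firth-penalised logistic regression and name the penalised likelihood-ratio test. The choice of test matters: six-term Firth with Wald tests and a Bonferroni split gave 2.3%, which is needlessly conservative;
- apply Holm across the two markers;
- label models from stepwise selection or the 4-step procedure as exploratory.

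The number of adjusters is the sponsor's choice. With all six terms, Firth with Holm gives 4.3%, and power falls by a further 1–3 points.

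The cost is SAP text, a restated power statement and some power. Simulated power with two adjusters:

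| Difference | 12/47, level 0.05 | 12/47, level 0.025 | 16/64, level 0.025 |
|---|---|---|---|
| Volume 0.285 cm³ | 87% | 79% | 91% |
| ADC 0.07 | 82% | 73% | 86% |
| ADC 0.065 | 77% | 67% | 82% |

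The 0.025 columns are the first Holm step. If both markers truly change (0.285 cm³ and 0.065), at least one is declared in about 90% of trials at 12/47 and 97% at 16/64. For 0.095 cm³, power at 12/47 and 0.025 is only about 10–12%. It is already about 19% for the plan's own t-test at 0.05, so the restated power should say which volume difference is intended.

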Evaluation of a Novel High-Resolution Diffusion-Weighted MRI Sequence

Study Intervention: High-resolution MRI

Funding Source: NIH

Amended version: 4/7/2020

Initial version: 1/8/2017

CONFIDENTIAL

This material is the property of Cedars-Sinai Medical Center. Do not disclose or use except as authorized in writing by the study sponsor.

Signature Page

The signature below constitutes the approval of this protocol and the attachments, and provides the necessary assurances that this trial will be conducted according to all stipulations of the protocol, including all statements regarding confidentiality, and according to local legal and regulatory requirements and applicable U.S. federal regulations and ICH guidelines.

Principal Investigator (PI) Name: _____

PI Signature: _____

Date: _____

CONFIDENTIAL

This material is the property of Cedars-Sinai Medical Center. Do not disclose or use except as authorized in writing by the study sponsor.

[figure not shown]
TABLE OF CONTENTS

| | |
|---|-----------|
| LIST OF ABBREVIATIONS | 1 |
| STUDY SCHEMA | 2 |
| STUDY SUMMARY..... | 2 |
| 1.0 STUDY ABSTRACT | 3 |
| 2.0 BACKGROUND AND RATIONALE | 4 |
| 3.0 STUDY DESIGN: | 5 |
| A. Overview..... | 5 |
| B. Study Population..... | 6 |
| C. Inclusion/Exclusion Criteria | 6 |
| D. Study endpoints | 6 |
| E. Study Design | 6 |
| F. Study Risks..... | 7 |
| G. Statistical Analysis | 9 |
| 4.0 REFERENCES..... | 10 |

LIST OF ABBREVIATIONS

| | |
|---------|--|
| ADC | Apparent diffusion coefficient |
| AS | Active surveillance |
| AUC | Area under the curve |
| DCE | Dynamic contrast enhanced |
| DWI | Diffusion-weighted imaging |
| EPI | Echo-planar imaging |
| hrMRI | High resolution MRI |
| mpMRI | Multiparametric MRI |
| MRI | Magnetic resonance imaging |
| PI-RADS | Prostate Imaging-Reporting and Data System |
| ROI | Region of interest |
| TRUS | Transrectal ultrasound |

STUDY SCHEMA

STUDY SUMMARY

| | |
|---------------------------------------|--|
| Title | Evaluation of a Novel High-Resolution MRI Sequence |
| Short Title | High resolution MRI |
| Protocol Number | |
| Phase | Not applicable |
| Methodology | Single arm, paired imaging |
| Study Duration | 3 years |
| Study Center(s) | Cedars Sinai Medical Center |
| Objectives | To determine if enhanced prostate imaging (high resolution MRI) will detect prostate lesions not seen on standard MRI. |
| Number of Subjects | 80 Study Subjects |

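### The hypothesis is that hrMRI change predicts biopsy progression, but section G plans only an association and no measure of discrimination

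*Combined protocol and SAP*

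**What the plan says.** The Study Summary states the hypothesis in predictive terms: imaging change "will predict presence of biopsy criteria for disease progression". Section 3.0 A (Overview) repeats this for hrMRI, and the Study Summary names the 12-core biopsy as the reference standard. Section 2.0 gives the motivation, conditionally: "If tumor growth kinetics or changes in grade determined by ADC prove prognostic, AS can rely less on serial transrectal biopsies". Section 1.0 words the hypothesis more weakly, as correlation with progression.

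The analysis is in section 3.0 G. A multivariable logistic regression is to study the "association between change in tumor size and ADC from the first and the second biopsy as assessed by imaging and disease progression", adjusted for baseline characteristics. The secondary analysis is the same association for single lesions. Backward and stepwise selection, a four-step selection procedure and model diagnostics follow, and the section ends there. The List of Abbreviations has an entry for "Area under the curve", but section G does not use it.

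The sample size rests on a comparison of mean change: "group sample sizes of 12 patients who progressed and 47 patients that do not progress achieve 91% power" for a "difference in the mean change tumor volume around 0.285 cm³", using a "two-sided two-sample t-test with a 0.05 level of significance".

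**The concern.** A test of a mean difference or of a regression coefficient asks whether the two groups differ on average. Prediction asks how far their distributions overlap, and so how many progressors a given imaging change would miss and how many non-progressors it would flag. The two questions can have quite different answers in the same data.

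If section G is followed exactly, the trial can report that imaging change is associated with progression without reporting how well it discriminates. Because the hypothesis speaks of prediction and the rationale of relying less on biopsy, readers may take a significant coefficient as support for both. An AUC added after the fact would not be a good substitute. With about 12 expected progressors and data-driven variable selection, an uncorrected AUC from the selected model would tend to be too high.

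**Working it through.** **Inputs.** All are from section 3.0 G unless noted.
- Group sizes: 12 progressors and 47 non-progressors; 20% progression.
- SD of a single volume measurement: 0.19 cm³. Correlation between the two measurements: 0 in the main calculation, 0.6 in the alternative.
- Difference in mean volume change: 0.285 cm³.
- ADC: SD 0.05, difference 0.07.
- Target sensitivity: none is given, so 80%, 90% and 95% are assumed.

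**Step 1. Reproduce the stated power.**
The SD of change is SD × √(2(1 − r)) = 0.19 × √2 = 0.2687 cm³ at r = 0. The standardized difference is d = 0.285 / 0.2687 = 1.061. Dividing by √(1/12 + 1/47) = 0.3234 gives 3.279. The normal approximation is Φ(3.279 − 1.960) = 0.906, and the noncentral t with 57 df gives 0.897. The Study Summary's figure ("59 patients achieve 91% power to detect a 0.285 cm^3 difference") is reproduced to within about one point, so d = 1.06 is the effect that the plan is powered for.

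**Step 2. Turn that effect into discrimination.**
Assume that changes are normal with equal SD in both groups. Then AUC = Φ(d/√2) = Φ(0.75) = 0.773.

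**Step 3. Precision of that AUC (Hanley-McNeil).**
With A = 0.7734:
- A(1 − A) = 0.1753 and A² = 0.5981
- A/(2 − A) = 0.6305 and 2A²/(1 + A) = 0.6745
- SE² = [0.1753 + 11 × (0.6305 − 0.5981) + 46 × (0.6745 − 0.5981)] / (12 × 47), so SE = 0.085
- 95% CI: 0.773 ± 1.96 × 0.085, about 0.61 to 0.94

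The Study Summary lists 80 subjects. If all were evaluable and 20% progressed (16 versus 64), the same formula gives SE 0.073 and a CI of about 0.63 to 0.92.

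**Step 4. Non-progressors flagged at an assumed sensitivity s.**
The share is 1 − Φ(d − z_s).

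| Assumed sensitivity | z_s | d − z_s | Non-progressors flagged |
|---|---|---|---|
| 80% | 0.842 | 0.219 | 41% |
| 90% | 1.282 | −0.221 | 59% |
| 95% | 1.645 | −0.584 | 72% |

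At 90% sensitivity and 20% progression, the negative predictive value is 0.8 × 0.413 / (0.8 × 0.413 + 0.2 × 0.1) = 0.94, against 0.80 with no test. About 35% of men would test negative.

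**Step 5. Other effects, at 90% sensitivity.**

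| Case | d | AUC | Non-progressors flagged |
|---|---|---|---|
| Plan's alternative: 0.18 cm³, r = 0.6 (SD of change 0.170) | 1.059 | 0.77 | 59% |
| ADC: 0.07, r = 0 (SD of change 0.0707) | 0.990 | 0.76 | 61% |
| Volume and ADC at their powered effects, if independent: √(1.061² + 0.990²) | 1.451 | 0.85 | 43% |
| 0.285 cm³ with r = 0.6 | 1.677 | 0.88 | 35% |
| Observed effect that just reaches p = 0.05 | 0.648 | 0.68 | 74% |

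A significant trial is therefore compatible with discrimination from weak to fairly good, and the planned output would not say which was found.

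**The case against.** The strongest reply is that this is an association study and section G tests an association. Section 1.0 speaks of changes that correlate with progression. The remark about biopsy in section 2.0 is conditional background. Every man is to have the reference biopsy, and nothing in the protocol proposes that a man forgo one on the strength of this trial. All of that stands. A reader might infer that the trial asks whether imaging can take the place of biopsy. The documents do not support that; they speak of prediction and, conditionally, of relying less on biopsy. The gap between the predictive hypothesis and an analysis that stops at association remains.

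A reader might also take 59% as what a significant trial would show. It is not. It holds only if the true effect equals the powered one, for volume alone, at a sensitivity that the documents do not set. The plan itself expects a positive correlation, and its model uses volume, ADC and baseline covariates together, so better discrimination is possible, as Step 5 shows.

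Two further cautions are fair. A baseline volume with mean and SD both 0.19 cm³ suggests skewness, so the normal model is only a guide. Section G also speaks of a 50% increase in volume, which could be read as 0.5 × 0.19 = 0.095 cm³ and would give worse figures. How that squares with 0.285 cm³ is a separate question, and this point does not depend on it.

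Finally, about 12 progressors are too few to pin down accuracy: detecting 11 of 12 has an exact 95% CI of 62% to 100%. That is a reason to show the interval, and a reason not to rest a conclusion on one estimated cut-off.

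**Conclusion.** The point holds in this form: the hypothesis is predictive, the planned analysis stops at association, and no measure of discrimination is specified. At the plan's powered volume effect the implied AUC is about 0.77 (95% CI about 0.61 to 0.94 with 12 versus 47). The share of non-progressors flagged is 41%, 59% or 72% at assumed sensitivities of 80%, 90% or 95%, and 35% at 90% sensitivity in the more favorable case of 0.285 cm³ with correlation 0.6. These figures assume normal changes with equal SDs and a single marker. They show that significance does not settle predictive value; they do not forecast the trial's result. The documents do not support concluding that hrMRI will discriminate poorly, or that the regression is invalid. The change should be made, but the planned association analysis can stand beside it.

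**What to change.** Keep the logistic regression and add the following to section G:

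- A pre-specified AUC of hrMRI change for progression on the 12-core biopsy, for volume, for ADC and for both together. Give a bootstrap 95% CI and an optimism correction in which any variable selection is repeated within each resample. State how men with no PI-RADS 3–5 lesion enter this analysis, since section G defines volume and ADC only from detectable lesions.
- Sensitivity, specificity and negative predictive value reported descriptively across a range of cut-offs. Where a cut-off is chosen from the data, the bootstrap intervals should include that choice; exact binomial intervals at such a cut-off would ignore it.
- A sentence saying that a significant coefficient alone will be reported as association and not as evidence that biopsies can be reduced.

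This needs SAP wording and a little more analysis of data already being collected, with no further patients, scans or biopsies. The downside is that the intervals will be wide and the result will look less favorable than a p-value alone.
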